1. INTRODUCTION

1.1 MEDICAL BACKGROUND

Despite the recent advancements in treatment, cancer remains a leading cause of death globally. In 2012 there were approximately 14 million new cancer cases and 8.2 million cancer-related deaths worldwide ([R15-3504](#)). In the majority of cases the disease is diagnosed in late, advanced stages and the vast majority of patients progress on available treatments and succumb to their disease. Therefore, there is a substantial need for novel therapeutic agents and treatment strategies to improve the treatment outcome for cancer patients.

Ligand-dependent Wnt signaling, mediated by LRP5 and LRP6, is highly activated in a subset of solid tumours (e.g. colorectal cancer [CRC], triple negative breast cancer [TNBC] and non-small cell lung cancer [NSCLC]). Activation leads to accumulation of intracellular β -catenin and expression of β -catenin dependent genes that promote cancer cell proliferation and resistance to chemotherapy/immunotherapy. An antagonistic paratopic antibody that binds LRP5 and blocks binding of Wnt ligands will block proliferation of malignant cells with activated Wnt signaling and increase sensitivity to immunotherapy. Therefore, the development of an LRP5 antagonist may constitute a valid therapeutic option against cancer and supports testing of BI 905681 in humans with the objective to improve patients' outcome. The first step in clinical development is this first in human trial to define the safety profile of BI 905681 and the Maximum tolerated dose (MTD)/ Optimal Biological Dose (OBD) for further development.

The most recent and more detailed information is available in the current Investigator's Brochure (IB) ([c27125909-01](#)).

1.2 DRUG PROFILE

1.2.1 Pharmacology

BI 905681 is a new biological entity consisting of three modules: two modules (bi-paratopic) binding to distinct epitopes of LRP5 and one module binding to human serum albumin (HSA) for half-life extension. The three modules are [REDACTED] connected by two peptide linkers. BI 905681 binds to LRP5 and blocks binding of Wnt ligands to the co-receptor complex, leading to inhibition of Wnt/ β -catenin signaling.

The Wnt ligands, which bind to LRP5 and Frizzled receptor leading to activation of downstream signaling, can be divided into Wnt1 class and Wnt3a class, each requiring different domains of LRP5 for signaling ([R17-1851](#)). In particular, BI 905681 antagonistically binds to these different domains of LRP5 receptor (bi-paratopic binding), thereby blocking Wnt signaling mediated by both Wnt1 and Wnt3a class ligands, leading to:

- Inhibition of LRP5 phosphorylation,
- Activation of β -catenin degradation complex formed by APC/Axin/GSK3 β ,

- Blockade of β -catenin nuclear translocation and binding to the TCF transcription factors, and
- Inhibition of transcription of Wnt/ β -catenin target genes.

Blockade of LRP5 phosphorylation and inhibition of transcription of Wnt/ β -catenin target genes (Axin2 and Notum), can be monitored *in vivo* as direct and indirect biomarkers for selective pathway engagement, respectively, in a Wnt driven tumor xenograft tissue ([n00267727](#)). Inhibition of Wnt target gene expression in tumor cells is necessary but not sufficient for antitumor efficacy (*in vitro* and *in vivo*), indicating that it represents a pharmacodynamic (PDc) biomarker, but not a biomarker of response to treatment with BI 905681. In mice PDc biomarker modulation can be monitored *in vivo* using skin as surrogate tissue via detection of Axin2 and Notum gene expression ([n00267728](#)).

LRP5 and LRP6 mediated Wnt pathway activation is regulated by the E3 ligase RNF43 and the secreted R-spondin proteins. RNF43 inhibits Wnt pathway activation by inducing the degradation of the Frizzled/LRP5 or LRP6 receptor complex via endocytosis. The RNF43 gene has been found to be frequently mutated/ inactivated in a subset of colorectal cancer (CRC) and pancreatic ductal adenocarcinoma samples ([R17-1850](#)). Furthermore, in a separate study, activating R-spondin fusion transcripts, leading to aberrantly inactivating RNF43 mutations have been shown to enhance ligand dependent Wnt signaling *in vitro* by increasing the abundance of Frizzled receptors on the cell surface.

Nonclinical proof of concept (inhibition of Wnt/ β -catenin signaling and efficacy) was demonstrated with BI 905681 in mechanistic Wnt-driven and disease-relevant models harbouring RNF43 mutations. In particular, BI 905681 demonstrated effective blockade of ligand-dependent Wnt signaling *in vitro* (RNF43 mutant pancreatic cancer cell lines and RNF43 mutant CRC patient-derived organoids) and *in vivo* models (Wnt driven breast cancer xenograft), as detected by reduction of Axin2 expression (and Notum gene expression in the *in vivo* model). Furthermore, BI 905681 demonstrated *in vitro* inhibition of cell viability and potent *in vivo* anti-tumor activity in the cancer models mentioned above. In contrast, BI 905681 did not block Wnt signaling (i.e. lack of inhibition of Axin2 expression) nor affect cell viability in RNF43 wild type pancreatic cancer cell and RNF43 wild type CRC patient derived organoid models, supporting the proposed patient enrichment biomarker strategy ([n00267725](#), [n00267729](#)).

1.2.2 Pharmacokinetics

The pharmacokinetics (PK) for BI 905681 were investigated in the cynomolgus monkey in a single dose PK and immunogenicity study and a repeat dose toxicokinetic (TK) and immunogenicity study. BI 905681 demonstrated dose-proportional increases in C_{max} and AUC with increasing dose levels in these studies. Human i.v. PK for BI 905681 was predicted using single species scaling from cynomolgus monkey to human using a Dedrick plot. The PK curves were fitted using a 2-compartment model.

Based on human PK parameter predictions and the minimal efficacious dose in the mouse MMTV-WNT1 breast cancer model, the predicted human therapeutic dose for BI 905681 is 1.4 mg/kg i.v. q1w. Alternatively, a less frequent dosing schedule can be chosen while keeping the C_{plasma} trough level constant, e.g. 3.5 mg/kg i.v. q2w or 6.6 mg/kg i.v. q3w.

1.2.3 Toxicology

The toxicity profile for BI 905681 has been assessed in repeat dose toxicity studies in monkeys and mice, an in vitro cytokine release assay, and an in vitro hemocompatibility study. The 4-week Good Laboratory Practice (GLP) repeat dose study in monkeys included safety pharmacology (cardiovascular, respiratory, and neurological function) and immunotoxicology endpoints.

A traditional tissue cross reactivity (TCR) study on cryosections of normal human tissues using immunohistochemistry was not conducted with BI 905681 due to the high nonspecific background staining of non-target-expressing cell types or non-cellular elements (e.g. interstitial matrix). However, a target tissue distribution study was conducted to determine the distribution of LRP5 in formalin-fixed, paraffin embedded human tissues. LRP5 staining was present in the stomach, small intestine, large intestine, salivary gland, endocrine pancreas, thyroid, kidney, ureter, urinary bladder, uterus, fallopian tube, placenta, testis, breast tissue, and brain. LRP5 staining was generally comparable between humans and cynomolgus monkeys.

The ready-to-use solution of BI 905681 (10 mg/mL in 25 mM acetate, 230 mM trehalose dihydrate, 0.05% (w/v) polysorbate 20, pH 5.5) demonstrated no hemolytic potential in human whole blood.

In repeat dose toxicity studies in monkeys, no mortality was observed. Once weekly intravenous administration of BI 905681 for up to 4 weeks (total 5 doses) and up to 150 mg/kg/dose in the cynomolgus monkey was well tolerated and resulted in no adverse findings in any of the parameters examined. In the 4-week repeat dose toxicity study, there were non-adverse trends for or slight decreases in bone formation markers (bone specific alkaline phosphatase (BAP) and/or procollagen type 1 amino-terminal propeptide (P1NP)) as a result of Wnt signaling inhibition by BI 905681, but no changes in bone resorption markers (β -Carboxy-terminal Telopeptide (β -CTx) and TRACP-5b) or microscopic correlates. The potential effect on bone mass can be monitored by serum bone biomarkers and bone densitometry assessment during the clinical development.

In addition, the implementation of an ophthalmologic monitoring plan is recommended if the patient displays visual symptoms during BI 905681 treatment.

The no-observed-adverse-effect level (NOAEL) was determined to be 150 mg/kg/dose q1w, and this dose is also considered as the highest non-severely toxic dose (HNSTD) in the 4-week monkey study. At 150 mg/kg/dose q1w, the steady state mean exposures were 5,290 μ g/mL (C_{max}) and 498,000 μ g•h/mL (AUC_{0-168h}). These exposures are 88X, 50X, and 31X (C_{max}), or 73X, 46X, and 29X (AUC_{0-168h}) to the estimated exposure at a 1.4 mg/kg q1w, 3.5 mg/kg q2w, and 6.6 mg/kg q3w therapeutic dose, respectively.

Collectively, the nonclinical package of pharmacology, pharmacokinetics, safety studies and data support the administration of BI 905681 to patients with advanced cancers. To date, no clinical trials have been conducted with BI 905681.

For a more detailed description of the BI 905681 profile please refer to the current IB.

1.3 RATIONALE FOR PERFORMING THE TRIAL

Based on the pre-clinical studies summarized in the previous section, the observed anti-tumour activity and safety profile warrant clinical testing of BI 905681 monotherapy in patients with advanced solid tumours. The therapeutic benefit or specific adverse events in patients cannot always be anticipated during the trial setup. As the trial progresses there may be new scientific knowledge about biomarkers and other factors contributing to diseases or the action of a drug.

1.4 BENEFIT - RISK ASSESSMENT

Most patients with locally advanced or metastatic tumours will succumb to their disease. Thus, there is a substantial need for novel therapeutic strategies to improve the outcome for patients with advanced or metastatic malignancies.

As BI 905681 is a first-in-class compound with no prior testing in humans, the risks of treatment have been evaluated based on the expected effects of targeting the Wnt pathway ([R17-4168](#)) and on the nonclinical toxicology data.

Under normal conditions, Wnt signaling, mediated by both LRP5 and LRP6 co-receptors, is required for (1) homeostasis of intestinal epithelial stem cells, located in the crypts of the small and large intestines; (2) skeletal development and homeostasis (promotion of osteoblast differentiation from progenitors and osteocyte survival); (3) retinal angiogenesis and regulation of retinal endothelial cell differentiation ([R17-1468](#), [R18-0131](#), [R18-1474](#), [R18-1475](#)); and (4) establishment of the hair follicle by activating bulge stem cells to progress toward hair formation. In preclinical mouse models (1) specific ablation of LRP5 in intestinal cells had no effect on intestinal epithelial cell homeostasis which is attributed to the compensatory role of LRP6-mediated Wnt signaling in the mouse intestinal development ([R17-1470](#)); and (2) specific ablation of LRP5 in mature osteoblasts showed reduced bone density, but the phenotype was more pronounced in the absence of both LRP5 and LRP6 with the development of severe osteopenia ([R18-0131](#)).

Several compounds targeting the Wnt pathway, but with a different mechanism of action compared to BI 905681 which selectively inhibits Wnt ligand dependent pathway activation, have been and continue to be studied in clinical trials. These compounds include vantictumab (anti-frizzled receptor antibody), ipafricept (frizzled 8 IgG fusion protein), rosmantuzumab (anti-RSPO3 antibody), Wnt-974 (cysteine palmitoyltransferase porcupine inhibitor) and ETC-159 (a selective small molecule porcupine inhibitor). Dysgeusia, fatigue, decreased appetite and gastrointestinal events including nausea, vomiting and diarrhoea were documented as frequent drug related adverse reactions ([R17-4166](#), [R17-4167](#), [R17-4168](#), [R18-1490](#)). In clinical studies of vantictumab, rosmantuzumab, ipafricept and ETC-159, bone toxicity was observed, consisting of changes in bone markers (increase in β -Carboxy-terminal Telopeptide [β -CTX] and/or decrease in procollagen type 1 amino-terminal propeptide [P1NP]), decrease in bone density as determined by bone densitometry, and fragility fractures

Proprietary confidential information © 2019 Boehringer Ingelheim International GmbH or one or more of its affiliated companies

that occurred late in the course of therapy ([R17-4166](#), [R17-4167](#), [R18-1420](#), [R18-1421](#), [R18-1490](#), [R18-1494](#)). To date, cytokine release syndrome and retinopathy have not been reported in any of these clinical studies.

A 4-week GLP monkey toxicology study revealed that BI 905681 at dose levels up to 150 mg/kg/dose q1w was very well tolerated with no adverse effects. Slight decreases of bone formation biomarkers (BAP and P1NP) were observed and were considered on target related effects. These changes were considered non-adverse based on minimal severity and lack of histopathology findings in bones. Bone resorption markers were not affected. No other on- or off-target effects of BI 905681 have been observed; thus, the no-observed-adverse-effect level (NOAEL) or the highest non-severely toxic dose (HNSTD) was determined to be 150 mg/kg/dose q1w in the monkey, the most relevant toxicology species.

It is anticipated that there may be adverse effects on the bone mass; thus, in this study potential AEs and symptoms (e.g. bone pain, back pain, reduced height, and pathologic fractures) will be monitored using regular monitoring of serum bone biomarkers and bone densitometry. In patients with documented pre-existing osteoporosis, treatment with vitamin D and/or calcium carbonate is recommended. Management guidelines and stopping rules for bone toxicity are provided (see Sections [3.1.1](#) and [4.1.6.4](#)).

Although the nonclinical GLP toxicology study of BI 905681 did not reveal a risk to induce cytokine release syndrome (CRS), patients will be monitored and guidelines for management of potential cytokine release syndrome are provided and must be followed thoroughly (see [Section 4.1.6.3](#)).

There were no BI 905681-related abnormal effects on the eyes (ophthalmological and microscopic examinations) observed in the 4-week repeat dose study in monkeys. Based on the published reports of a potential risk of retinal toxicity as a result of Wnt pathway inhibition, an ophthalmologic status assessment will be performed at baseline in all patients. In case of occurrence of visual symptoms (e.g. loss in visual acuity, blurred or distorted vision, floating specks or cobwebs, night vision changes or colour vision changes) the same ophthalmologic assessment will be repeated. Guidelines for management of potential retinal toxicity are provided (see [Section 4.1.6.5](#)). Monitoring of asymptomatic patients with spectral domain optical coherence tomography (SD-OCT) and full ophthalmologic exams is not needed based on published literature. The published literature of related competitors do not include retinopathy or any other retinal toxicity as drug-related adverse event.

Throughout the study the safety of the participants will be monitored regularly by a Safety Monitoring Committee (SMC). The assessments planned in this study are standard for oncology patients.

Although rare, a potential for drug-induced liver injury (DILI) is under constant surveillance by sponsors and regulators. Therefore, this trial requires timely detection, evaluation, and follow-up of laboratory alterations in selected liver laboratory parameters to ensure patients' safety, see also [Section 5.2.6](#), adverse events of special interest.

Proprietary confidential information © 2019 Boehringer Ingelheim International GmbH or one or more of its affiliated companies

In summary, the nonclinical safety package and data support the administration of BI 905681 to patients with advanced or metastatic cancer, although close monitoring of all adverse events with a focus on potential on-target adverse events is warranted. Given the unmet medical need of these patients, there is a case for potential benefit offered by this novel mode of action with acceptable risk.

2. TRIAL OBJECTIVES AND ENDPOINTS

2.1 MAIN OBJECTIVES, PRIMARY AND SECONDARY ENDPOINTS

2.1.1 Objectives

The primary objective of this trial is to determine the maximum tolerated dose (MTD)/optimal biological dose (OBD) of BI 905681 given as an intravenous infusion and to determine the recommended dose and dosing schedule for further trials in the development of BI 905681. The MTD will be defined based on the frequency of patients experiencing dose-limiting toxicities (DLTs) during the MTD/DLT evaluation period, which is defined as the first cycle of treatment. Separate MTDs will be determined for Schedule A and Schedule B.

The secondary objective of the trial is to determine the pharmacokinetic (PK) profile of BI 905681.

2.1.2 Primary endpoint(s)

[figure not shown]
The primary endpoints of the trial are:

- The MTD/OBD of BI 905681. The MTD will be assessed based on the number of patients experiencing DLTs, graded according to Common Terminology Criteria for Adverse Events (CTCAE) Version 5.0, in the first cycle of treatment (3 weeks in Schedule A and 4 weeks in Schedule B). The MTD is defined as the highest dose with less than 25% risk of the true DLT rate being equal to or above 33%. Separate MTDs will be determined for Schedule A and Schedule B
- Number of patients experiencing adverse events (AEs) during the entire treatment period

2.1.3 Secondary endpoint(s)

The secondary endpoints of the trial are:

- The following PK parameters of BI 905681 will be evaluated after the first administration of BI 905681 (if feasible):
 - C_{max} : maximum measured concentration of BI 905681 in serum after first infusion
 - AUC_{0-t_z} : area under the serum concentration-time curve over the time interval from 0 to the last measured time point (t_z)

3. DESCRIPTION OF DESIGN AND TRIAL POPULATION

3.1 OVERALL TRIAL DESIGN AND PLAN

This is a Phase I, open-label, non-randomised study of BI 905681 administered intravenously as a single agent.

[figure not shown]

Figure 3.1: 1 Trial Design

The design of the trial allows an escalation of dose with intensive safety monitoring to ensure the safety of the patients.

A Bayesian logistic regression model (BLRM) with overdose control ([R13-4803](#)) will be used to determine the MTD estimate. The BLRM estimates the MTD by updating estimates of the probability of observing a DLT for each dose level. At any time in the trial, it will not be permitted to escalate to a dose which does not fulfil the escalation with overdose control (EWOC) principle (for further details refer to [Section 7](#)).

The trial aims to test two different dosing schedules for BI 905681 (every 3 weeks (q3w) in a 3-week cycle and every 2 weeks (q2w) in a 4-week cycle) with two separate BLRM models; in Schedule A the cycles will be 3 weeks in duration and in Schedule B the cycles will be 4 weeks in duration. Recruitment into each dosing schedule will occur sequentially.

Recruitment into Schedule B will start after the MTD/OBD of Schedule A is reached. The

starting dose in Schedule B will be determined by the SMC. The SMC will also review whether the planned dosing schedule, assessments and sample collection in Schedule B remain appropriate, and may decide not to pursue testing of another Schedule. Within each treatment cohort, patients will be treated at least 72 hours apart to allow adequate monitoring for CRS and implementation of preventive measures if required.

In each schedule, successive cohorts of patients will receive increasing doses of BI 905681 until the MTD/OBD is reached. Dose escalation steps will depend on the observed AEs and occurrence of DLTs during the first treatment cycle. However, relevant safety information from all treatment cycles will be considered for the determination of the MTD/OBD and recommended dose for further development. In each dose cohort a minimum of 2 patients will be treated until a first AE of CTCAE Grade ≥ 2 occurs during the DLT evaluation period (the first cycle of treatment), excluding AEs which are clearly related to disease progression or concurrent illness. In that case a minimum of 3 patients will be treated at the recruiting cohort and subsequent dose cohorts. The SMC may also recommend the size for the next dose escalation cohort or recommend expanding the size of the recruiting cohort.

Starting at dose Cohort 2 the aim is to recruit a minimum of 2 patients with solid tumours harbouring the RNF43 mutation or R-spondin fusion. In case fewer than 2 patients harbouring the RNF43 mutation or R-spondin fusion can be recruited to the current dose cohort, additional patients harbouring the RNF43 mutation or R-spondin fusion will be recruited as “back-filled” cohorts. Patients included in the “back-filled” cohorts will be treated at a dose level below the current dose level being investigated. These patients will be used to permit correlation between exposure and PDc effects. The safety data from the “back-filled” patients will be evaluated additionally in a descriptive manner and provided to the SMC.

As soon as all patients enrolled for safety evaluation on a dose level have completed the MTD evaluation period, a BLRM with overdose control will be applied using all available data (from both the main cohorts and the “back-filled” cohorts) to determine the next permitted dose level and evaluate MTD. The overdose risk will then be calculated for each preliminary dose level from [Table 4.1.3: 1](#) and dose escalation will be permitted to all doses which fulfil the EWOC criterion. Specifications and details of the BLRM are depicted in [Section 7.1](#) and [Appendix 10.3](#). At the end of each dose level, based on the model and on additional information (PK, pharmacodynamics, patient profiles), the members of the SMC will reach a joint decision on the next dose level to be investigated.

In case an MTD cannot be determined, and pharmacometric modelling and simulation has demonstrated that the dose levels reached provide the required exposure over the dosing interval, the SMC can decide to stop dose escalation and recommend a dose for further clinical development.

If DLTs are observed in the first two consecutive patients of a previously untested dose level, subsequent enrolment to that cohort will be stopped. The BLRM will be re-run to confirm that the dose level still fulfils the EWOC principle. Based on this information, the SMC will evaluate whether the next patients will be enrolled at the same dose level, or if they will be

enrolled at a lower dose level. After the criterion for MTD is fulfilled, there will be no further dose escalation regardless of the SMC recommendation.

If no DLT is observed, the SMC may decide to declare the Recommended Dose for Expansion (RDE) based on PK/pharmacodynamics endpoints and overall safety profile. Any DLTs occurring after the start of the second cycle will be considered for the evaluation of the RDE for BI 905681. The SMC can declare any dose fulfilling the EWOC criterion as the RDE, independent of the MTD estimate.

Patients will continue to receive treatment with BI 905681 until disease progression (PD) according to RECIST or until another reason requiring termination of treatment (see [Section 3.3.4](#)).

After completion of the dose escalation and determination of the MTD/OBD, a protocol amendment is planned to add expansion cohorts to the trial.

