4.1.3 Dose-escalation scheme

Table 4.1.3: 1 Provisional (Example Only) dose levels for escalation in Schedule A

Dose Level	Proposed dose	Increment from previous dose
1	1.0 mg/kg/q3w	Starting dose
2	2.5 mg/kg/q3w	150%
3	4.5 mg/kg/q3w	80%
4	6.5 mg/kg/q3w	44.4%
5	8.5 mg/kg/q3w	30.8%

At the end of each treatment cohort, BI will convene a meeting with the SMC members. At the dose escalation meeting, the clinical course (safety information including both DLTs and all CTCAE Grade ≥ 2 toxicity data during the DLT evaluation period, and all available PK data) for each patient in the current dose cohort will be described in detail. Updated safety data on other ongoing patients, including data beyond the DLT evaluation period, will be discussed as well. Based on that, a decision on the next dose level to be tested is to be made. Dose escalation will continue until identification of the MTD/OBD, safety concerns arise, or the trial is terminated for other reasons. The absolute maximum clinical dose must not exceed 1120 mg/dose.

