4.1.4 Starting Dose for Schedule B

After determination of the MTD/OBD in Schedule A, Schedule B will commence. The starting dose in Schedule B will be determined by the SMC, and will not exceed 30% of the MTD from Schedule A. The SMC will also review whether the planned dosing schedule, assessments and sample collection in Schedule B remain appropriate, and may decide not to

pursue testing of this schedule. Schedule B will utilise its own BLRM and prior distribution will be derived from data in Schedule A.

The dose levels and cohort sizes in Schedule B will be decided by the SMC, following the same process and rules as for Schedule A (described in [Section 3.1](#)). The absolute maximum clinical dose must not exceed 1120 mg/dose.

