7. STATISTICAL METHODS AND DETERMINATION OF SAMPLE SIZE

7.1 STATISTICAL DESIGN - MODEL

The trial will be performed as an open-label study. The objective of the design is to determine the MTD of BI 905681 defined as the highest dose with less than 25% risk of the true DLT rate being $\geq 33\%$ (EWOC criterion). The dose-finding in Schedule A and B will be guided by Bayesian 2-parameter logistic regression models with overdose control ([R13-4803](#)). Separate MTDs will be determined for Schedule A and Schedule B.

The model is given as follows:

$$\text{logit}(\pi_d) = \log(\alpha) + \beta * \log(d/d^*),$$

where $\text{logit}(\pi) = \log(\pi/(1-\pi))$.

π_d represents the probability of having a DLT in the MTD evaluation period at dose d , $d^* = 4.5 \text{ mg/kg/week}$ is the reference dose, allowing for the interpretation of α as the odds of a DLT at dose d^* , and $\theta = (\log(\alpha), \log(\beta))$ with $\alpha, \beta > 0$ is the parameter vector of the model.

The estimated probability of a DLT at each dose level from the model will be summarised using the following intervals:

Under dosing: [0.00, 0.16]

Targeted toxicity: [0.16, 0.33]

Over toxicity: [0.33, 1.00]

The BLRM recommended dose for the next dose level is the level with the posterior probability of the DLT rate falling in the target interval [0.16, 0.33] without skipping any dose level. Applying the EWOC criterion it should be unlikely (<25% posterior probability) that the DLT rate at that dose will exceed 0.33.

The MTD may be considered reached if all the following criteria are fulfilled:

1. Next recommended dose = current dose (stabilisation condition)
2. Number of DLTs in study is at least 1.
3. At least 9 patients have been treated in the trial.

and at least one of the following criteria is fulfilled:

- The posterior probability of the true DLT rate in the target interval [0.16 – 0.33] of the MTD is above 0.5, OR
- At least 6 patients have been treated at the MTD.

The SMC may recommend stopping the trial after the criterion for MTD is fulfilled. Further patients may be included to confirm this MTD estimate. If no DLT is observed while information from the PK profile is considered sufficient, the SMC may recommend a dose for further testing. Any DLTs occurring after the start of the second cycle will be considered for the evaluation of the recommended dose for further testing for BI 905681.

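### Section 3.1 permits escalation to every dose that passes EWOC, while Section 7.1 has the model recommend without skipping a level: after 0/2 DLTs at 1.0 mg/kg the highest doses are 8.5 and 2.5 mg/kg

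*Protocol*

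**What the plan says.** **Escalation steps.** Protocol Section 3.1 has the overdose risk calculated for each provisional dose in Table 4.1.3: 1, after which "dose escalation will be permitted to all doses which fulfil the EWOC criterion". It gives no step limit. It also says that "it will not be permitted to escalate to a dose which does not fulfil the escalation with overdose control (EWOC) principle", and it sends the reader to Section 7.1 and Appendix 10.3 for the model ("Specifications and details of the BLRM are depicted in" those places).

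Section 7.1 describes the recommended next dose as the level with the posterior probability of the DLT rate falling "in the target interval [0.16, 0.33] without skipping any dose level", subject to EWOC: less than 25% posterior probability of a DLT rate of 0.33 or more. Section 11.1 gives the reason for that wording, namely to make clear that no level would be skipped. In Appendix 10.3, scenario 1, the next permitted dose after clean cohorts at 1.0 and 2.5 mg/kg is 4.5 mg/kg. The same appendix leaves the actual dose to the SMC, with the model's recommendation as one consideration.

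For Schedule B, Section 4.1.4 applies the "same process and rules as for Schedule A" and points to Section 3.1.

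**Two DLTs at a new level.** If the first two patients of an untested level both have DLTs, Section 3.1 stops enrolment to that cohort and re-runs the model to confirm that the level still fulfils EWOC. Then "the SMC will evaluate whether the next patients will be enrolled at the same dose level" or at a lower one. It does not say what happens if the level fails.

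**The concern.** An SMC member working from Section 3.1 and one working from Section 7.1 could reach different sets of allowable doses from the same cohort data. This is a first-in-human trial whose prior, by Section 7.1, carries the information of about 1.8 patients. EWOC alone may therefore restrain the first steps very little, and a step limit, if one is meant, would do most of the work. The minimum cohort is 2 patients until a first Grade 2 or higher AE, so the question can arise after two patients.

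The second question is whether a level that fails the EWOC re-check can still receive patients. The only express EWOC prohibition on assigning patients is worded for escalation.

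**Working it through.** **Inputs.** The model is logit(p) = log(α) + β·log(d/4.5) (Section 7.1). The prior on (log α, log β) is the three-component normal mixture of Table 7.1: 1: weights 0.9, 0.05 and 0.05; means (−2.701, −0.233), (−0.973, −0.115) and (−4.101, −1.113); SDs (2, 1), (2, 1) and (5, 0.01); correlations 0. P(OD) is the posterior probability that p ≥ 0.33, and EWOC requires P(OD) < 0.25. Posteriors were obtained by grid integration over ±6 SD per component with a binomial likelihood.

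Two readings had to be assumed. The reference dose is printed per week, but 4.5 on the q3w scale reproduces the tables. The patient counts in Table 10.3: 1 did not survive extraction, so cohorts of 3 were taken from the accompanying text (9 patients over three cohorts).

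**Step 1: reproduce the protocol's prior table and its updated data.**

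| Dose (mg/kg) | 1.0 | 2.5 | 4.5 | 6.5 | 8.5 |
|---|---|---|---|---|---|
| Prior P(OD), Table 7.1: 2 | 0.072 | 0.114 | 0.177 | 0.244 | 0.295 |
| Recomputed | 0.074 | 0.117 | 0.179 | 0.247 | 0.299 |
| After 0/2 at 1.0 | 0.018 | 0.048 | 0.107 | 0.180 | 0.236 |

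Across scenarios 1 to 10 of Table 10.3: 1, every stated P(OD) is reproduced within 0.010, and every EWOC pass or fail agrees.

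**Step 2: apply each rule to 0/2 at 1.0 mg/kg.** All five doses are below 0.25.
- Section 3.1, literally: every dose up to 8.5 mg/kg is permitted.
- Section 7.1: the recommendation can be no higher than 2.5 mg/kg, P(OD) 0.048.

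Before any data, 8.5 mg/kg fails EWOC (0.295), so two clean patients are enough to bring it inside. The margin is narrow (0.25 − 0.236 = 0.014). Adding the largest discrepancy from the protocol's tables gives 0.236 + 0.010 = 0.246, which still passes. With 0/3 the figure is 0.222.

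**Step 3: which sense does the appendix use?** For scenario 1 (0/3 at 1.0 and 0/3 at 2.5) the recomputed P(OD) is 0.112 at 6.5 and 0.168 at 8.5. Both pass EWOC, yet the appendix names 4.5 as the next permitted dose. It therefore follows Section 7.1, not the literal text of Section 3.1.

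**Step 4: two DLTs in the first two patients of a new level.** P(OD) at that level, with no DLTs at any lower level:

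| Patients per lower level | 1.0 | 2.5 | 4.5 | 6.5 | 8.5 |
|---|---|---|---|---|---|
| 2 | 0.83 | 0.62 | 0.63 | 0.70 | 0.64 |
| 3 | 0.83 | 0.54 | 0.57 | 0.67 | 0.56 |
| 6 | 0.83 | 0.39 | 0.50 | 0.64 | 0.43 |

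Every entry fails EWOC. This is not universal: 15 clean patients at 1.0 followed by 2/2 at 2.5 gives 0.220, which passes. In Appendix 10.3, scenarios 2 and 10, the current dose fails (0.433 and 0.477) and the next dose is lower.

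**The case against.** The best defence is that Section 3.1 should not be read alone. It refers to Sections 7 and 7.1 and Appendix 10.3; its own paragraph also speaks of a single next permitted level; the amendment's reason is explicit; and each step needs a joint SMC decision that also weighs PK, pharmacodynamics and patient profiles. This shows what was probably intended. It does not remove the conflict. The no-skip words govern what the model recommends, the recommendation is one input to the SMC, and the sentence on what is permitted still has no step limit.

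Three stronger readings are tempting, and the documents do not support them.
- A reader might infer that EWOC restricts escalation only, so that the protocol allows continued dosing at a rejected level. Section 3.1 itself orders an EWOC check of the current level after two DLTs; Section 7.1 applies EWOC to the recommended next dose, which can be the current one; and scenarios 2 and 10 step down. What remains is an unstated consequence, not a permission.
- A reader might take the move from 2.5 to 5.0 mg/kg in SAP Table 6.1: 1 as a skipped level. The protocol's table is headed "Provisional (Example Only) dose levels for escalation in Schedule A", and 5.0 takes the place of the provisional 4.5. The SAP sequence (1.0, 2.5, 5.0, 7.0, 8.5) shows no skip.
- A reader might quote the chance of two clean patients under the protocol's High Tox scenario (0.89² = 0.79) or Extremely High Tox scenario (0.72² = 0.52) as the risk of an 8.5-fold step. Those are only the probabilities of the starting data. The step would still need an SMC decision.

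**Conclusion.** The inconsistency on escalation steps holds. From 0/2 DLTs at 1.0 mg/kg, Section 3.1 taken literally permits 8.5 mg/kg (P(OD) 0.236), while Section 7.1 recommends at most 2.5 mg/kg. Because it concerns a safety rule in a first-in-human trial, it should be corrected.

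The secondary gap also holds in a limited form: the re-check after two DLTs is required, but the result of failing it is not stated, and it fails in all the constellations tabulated above (0.39 to 0.83).

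The figures rest on the Schedule A prior, the q3w reading of the reference dose, and the cohort sizes shown. They do not transfer to Schedule B, which was to have its own model and a prior still to be derived, although Section 4.1.4 would carry the Section 3.1 wording into it. The finding concerns the written plan. The SAP reports that the trial ended before Schedule B began, and nothing in it suggests a jump from 1.0 to 8.5 mg/kg.

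**What to change.** Reconcile Sections 3.1, 4.1.4 and 7.1 and Appendix 10.3 with the reason stated for Amendment 1 in Section 11.1, so that one rule on permitted escalation steps applies throughout and the word permitted has one meaning. Separately, reconcile the two-DLT paragraph of Section 3.1 with the EWOC statement earlier in that section, with Section 7.1 and with scenarios 2 and 10, so that the consequence of a current dose failing the re-check is stated. Which dosing rule applies is for the sponsor to decide and write down.

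The cost is a few sentences of protocol text, with no extra patients or procedures.
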